## DISCUSSION

This prospective, randomized, open-label clinical study evaluated the use of an intracanalicular 0.4 mg dexamethasone insert in combination with topical cyclosporine 0.05% for the treatment of dry eye. Although the efficacy of this combination remains unclear based on the results of this pilot study, the results of this study support the safety of this approach without any adverse events, no IOP spikes above baseline and no device-related complications.

Topical cyclosporine 0.05% has been shown to provide an improvement in tear production and dry eye-related symptoms but many patients in clinical trials leading to its approval reported a delay in symptomatic relief. As a delay in relief can contribute to reduced compliance, providers may initiate adjuvant use of topical steroids in combination with topical cyclosporine 0.05% and studies evaluating this combined regimen reported findings of quicker symptomatic relief and more rapid improvement of objective parameters such as Schirmer testing and corneal staining. No groups in this study met the primary endpoint, however, patients in the loteprednol group reported a significant improvement in symptoms as measured by the DEQ-5 questionnaire, consistent with prior studies evaluating the combined use of corticosteroids and topical cyclosporine 0.05%. The dextenza group also noted an improvement in symptoms, but the change was not statistically significant. An improvement in symptoms with a combination of cyclosporine 0.05% and corticosteroids corroborates what has previously been reported.

Several prior studies have highlighted the safety and efficacy of the dexamethasone insert evaluated in this present study with regards to postoperative pain and inflammation following cataract surgery. However, multiple recent studies have described use of the insert beyond the postoperative setting including a recent report describing the combined use of thermal pulsation therapy with the dexamethasone insert for the treatment of meibomian gland dysfunction. To our knowledge, this is the first study evaluating the adjuvant use of the dexamethasone insert in combination with cyclosporine 0.05%. Although this present study did not yield any significant results, we anticipate future studies will involve the dexamethasone insert evaluating its utility in the treatment of dry eye.

Prior studies have demonstrated the favorable use of topical corticosteroids as an induction agent in combination with topical cyclosporine to augment the anti-inflammatory properties offered by cyclosporine. Although both the topical steroid and intracanalicular dexamethasone groups in this present study offered similar results, there are considerations unique to corticosteroids as it relates to sustained drug delivery. The sustained-release insert described herein offers theoretical benefits to bypass the challenges and potential side effects of topical corticosteroids. Topical agents, which are instilled intermittently, inevitably lead to variability in drug concentration owing to the poor bioavailability of the agent. The insert's intracanalicular location, with close proximity to the ocular surface, purports to offer a superior bioavailability profile with improved consistency of drug concentration in contrast to topical administration. The tapered delivery of drug from the insert over the course of 30 days minimizes the risk for rebound inflammation, which can occur with abrupt discontinuation of topical steroids. In addition, the preservative-free composition of the insert overcomes concerns related to preservatives and ocular surface toxicity, an established issue related to long-term use of topical drops.

This study has a number of limitations. The sample size was small in each group. The primary endpoint, which was improvement in corneal staining, was not met by any of the three groups. However, it is important to note that corneal staining was not a component of the inclusion criteria and thus future studies with refined inclusion criteria would be beneficial to evaluate the value of dexamethasone combined with cyclosporine 0.05% in improving corneal staining. Further, it's possible that an increase in sample size and an adequately powered study could lead to meaningful changes in other parameters such as TBUT and Schirmer scores, both of which have been demonstrated to improve following use of cyclosporine 0.05% in prior studies.

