## **RESULTS**

### **Patient Demographics**

Sixty eyes of 30 subjects were successfully enrolled into the study including 20 eyes of 10 subjects in the dexamethasone/cyclosporine group, 22 eyes of 11 subjects in the loteprednol/cyclosporine group and 18 eyes of 9 subjects in the cyclosporine monotherapy group. All 3 groups were summarized by baseline characteristics, which are shown in Table 2.

None of the three groups, including the study and two control groups met the primary endpoint. In the dextenza group, the mean baseline corneal staining score was  $0.5 \pm 1.0$  with 70% ( $n=14$ ) without evidence of corneal staining at baseline. The mean score at weeks 4, 8 and 12 was  $0.6 \pm 1.0$  ( $P = 0.99$ ),  $0.5 \pm 1.1$  ( $P = 0.99$ ) and  $0.7 \pm 1.4$  ( $P = 0.97$ ), respectively. In the loteprednol group, the mean baseline corneal staining score was  $0.8 \pm 1.5$  with 64% ( $n=14$ ) without corneal staining at baseline. At weeks 4, 8 and 12, the mean score was  $0.9 \pm 0.9$  ( $P = 0.99$ ),  $0.0 \pm 0.0$  ( $P = 0.06$ ) and  $0.6 \pm 1.0$  ( $P = 0.78$ ), respectively. In the cyclosporine monotherapy group, the mean baseline corneal staining score was  $0.5 \pm 0.5$  with 50% ( $n=9$ ) of eyes absent of any corneal staining at baseline. There was no significant change in corneal staining at any time point with a mean score of  $1.1 \pm 1.4$  ( $P = 0.26$ ),  $0.3 \pm 0.6$  ( $P = 0.63$ ) and  $0.5 \pm 0.7$  ( $P = 0.99$ ) at weeks 4, 8 and 12, respectively. These results, in addition to comparisons of other outcome measures, are summarized in Table 3.

There was no significant change in conjunctival staining, Schirmer scores, TBUT, tear osmolarity or meibomian gland scores at any of the follow-up time points in comparison to baseline in all three groups. These results are summarized and also demonstrated in Table 3.

Across all visits, the mean IOP remained stable in all three groups. In the cyclosporine monotherapy group, there were no instances of IOP elevation  $>10$  mmHg above baseline. Similarly, in the dextenza and loteprednol groups, there were no instances of IOP elevation  $>10$

mmHg above baseline at any time point. There were no canalicular-related complications or adverse events related to implantation of the dexamethasone insert. No patients required removal of the insert.

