## CONCLUSION

The challenges of topical medication use are widespread and well recognized across ophthalmology. The safety profile reported in this study, albeit a small sample size, indicates the dexamethasone intracanalicular insert is a safe alternative option to topical steroids to augment the anti-inflammatory properties of topical cyclosporine 0.05%. Further study is necessary but use of the dexamethasone insert may provide a means to optimize medication delivery without compromising safety or efficacy in the treatment of dry eye disease.

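### The report's safety conclusions are wider than its safety results, and its baseline IOP row duplicates tear break-up time

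*SAP*

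**What the plan says.** The report's safety results stand in one paragraph of the SAP's Results, under Patient Demographics:

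- On the device: "There were no canalicular-related complications or adverse events related to implantation of the dexamethasone insert".
- On removal: "No patients required removal of the insert".
- On average IOP: "Across all visits, the mean IOP remained stable in all three groups".
- On individual IOP rises: none above 10 mmHg over baseline with monotherapy, and likewise "in the dextenza and loteprednol groups, there were no instances of IOP elevation" beyond that same threshold.

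The Discussion opens its safety sentence with "Although the efficacy of this combination remains unclear based on the results of this pilot study" and goes on to say that the results "support the safety of this approach without any adverse events, no IOP spikes above baseline and no device-related complications". The Conclusion reads: "The safety profile reported in this study, albeit a small sample size, indicates the dexamethasone intracanalicular insert is a safe alternative option to topical steroids". Caveats are present. The Discussion admits "The sample size was small in each group", and the Conclusion asks for more study.

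On data collection, the SAP's Main Outcome Measures section says that AEs reported by subjects were recorded at every visit. The protocol's Schedule of Events (5.1) lists IOP and subject-reported AEs at all six visits. Its AE row is labelled as referring to the time after insertion, whereas the visit lists in 5.1.1 carry no such limit. Protocol 5.1.3 has the investigator record every AE, while 6.2 restricts recording to events judged medically relevant.

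**The concern.** Efficacy is described as unclear and no arm met the primary endpoint, so safety is the report's main positive message. Two qualifiers in the Results disappear on the way to the Discussion: the limitation to implantation-related AEs, and the 10 mmHg threshold. The Conclusion then sets the insert beside topical steroids, although no AE result is given for the loteprednol arm and the Statistical Analysis section describes no safety analysis and no comparison between arms. A reader would come away believing that no AE of any kind occurred and that safety relative to topical steroids had been examined. The Results show neither. The one table row that could help a reader judge IOP also appears to hold another variable's values.

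**Working it through.** Neither document gives an AE rate, a safety margin or a sample-size calculation, so there is no stated figure to reproduce.

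**Step 1. Discussion and Conclusion against Results.**

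- No device-related complications: matched by the absence of canalicular complications, implantation-related AEs and removals. Supported.
- No AEs at all: the Results cover implantation-related AEs only. There is no all-AE count for any arm, and the safety paragraph cites no table. Unsupported.
- No IOP spikes: the Results cover rises above 10 mmHg. Smaller rises are not reported, and a spike is not defined. Wider than the result.
- Safe alternative to topical steroids: the only individual-level safety outcome reported for both the insert and loteprednol arms is the zero count of IOP rises above 10 mmHg.

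**Step 2. What a zero count can show.** Inputs are the arm sizes in the Results: 10 insert, 11 loteprednol and 9 monotherapy patients. The patient is the unit because two eyes of one person are not independent. I assume that every enrolled patient was assessed. The exact two-sided 95% upper limit for 0/n is 1 − 0.025^(1/n):

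- n = 10: 1 − 0.025^(1/10) = 0.308
- n = 11: 1 − 0.025^(1/11) = 0.285
- n = 9: 1 − 0.025^(1/9) = 0.336

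Treating the 20 insert eyes as independent, which is optimistic, would still give 1 − 0.025^(1/20) = 0.168. As an illustration with assumed rates, a true patient-level rate of 10% yields no events in 10 patients with probability 0.9^10 = 0.35. A rate of 20% does so with probability 0.8^10 = 0.11.

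**Step 3. Insert against loteprednol, IOP rise above 10 mmHg.** With 0/10 and 0/11, each Wilson upper limit is z²/(n + z²), where z² = 3.84:

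- insert: 3.84/13.84 = 0.278
- loteprednol: 3.84/14.84 = 0.259

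Both observed proportions are zero, so the Newcombe 95% interval for insert minus loteprednol is −25.9 to +27.8 percentage points.

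**Step 4. The IOP row.** Baseline IOP in SAP Table 1 (mmHg) against baseline tear break-up time in SAP Table 2 (seconds):

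- insert: 6.6 ± 2.2 and 6.6 ± 2.2
- loteprednol: 5.4 ± 1.5 and 5.4 ± 1.5
- monotherapy: 5.7 ± 3.3 and 5.7 ± 3.3

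Six of six figures agree across two unrelated measurements, so at least one row is wrong. The break-up-time baseline fits its own follow-up series. The changes at months 1, 2 and 3 are +1.4, +1.1, +1.1 (insert), +0.7, +0.8, +0.7 (loteprednol) and +1.7, +1.4, +1.6 seconds (monotherapy), and the Results call them non-significant. The IOP row is therefore the likelier error. No other IOP mean is given, so the statement about steady mean IOP cannot be checked.

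**The case against.** The strongest defence is that nothing in the documents contradicts the Discussion. Subject-reported AEs were recorded at each visit, so its sentence may simply be the all-AE result stated in the wrong section. Spikes may be shorthand for the 10 mmHg criterion used a page earlier. The Conclusion makes no formal claim of equivalence or non-inferiority on safety, and it carries a sample-size caveat and a call for more work.

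Much of this stands. The claim of no AEs is missing its support and is not refuted. If spikes is shorthand, restating the threshold costs a few words. The caveats are real, but they put no size on the uncertainty and do not supply comparator AE data.

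Three stronger readings are tempting and should be resisted.

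- A reader might infer that AEs occurred and were left out, especially as protocol 6.2 filters what is recorded. No document shows an omitted AE. Because subject-reported events were recorded, the doubt lies mainly with events observed by the investigator.
- A reader might infer that the duplicated row invalidates the count of IOP rises above 10 mmHg. That count can come from patient-level data and need not depend on the row.
- A reader might take the wide intervals as evidence of harm. They show only how little 10 patients can exclude.

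**Conclusion.** The point holds as a reporting fault that should be corrected. Two of the three safety phrases in the Discussion go beyond the Results, and the Conclusion's comparison with topical steroids has no AE result from the loteprednol arm behind it. Even a confirmed zero among 10 insert patients leaves patient-level rates up to 30.8% open. For IOP rises above 10 mmHg the comparison with loteprednol is uncertain by about 26 to 28 points either way. These figures rest on all enrolled patients having been assessed and on the patient as the unit. That at least one of the duplicated rows is wrong follows from the tables. That it is the IOP row is a judgement from the break-up-time series.

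Two protocol points are secondary and change no data already collected. Sections 5.1.3 and 6.2 conflict on which AEs are recorded and must be reconciled. Section 5.1.3 also refers to Section 7 for judging severity and relationship to treatment, but Section 7 covers only baseline variables. The second point bears on this report because its only AE result depends on a judgement of relatedness.

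**What to change.** In the report:

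1. Limit the Discussion and Conclusion to the outcomes in the Results, and restate the 10 mmHg threshold wherever IOP rises are mentioned.
2. Give zero counts per patient with exact two-sided 95% intervals for the arm concerned. Insert outcomes: 0/10, 0 to 30.8%. IOP rise above 10 mmHg: 0/10 insert, 0 to 30.8%; 0/11 loteprednol, 0 to 28.5%; 0/9 monotherapy, 0 to 33.6%. State how many patients were assessed, and recompute if any were not.
3. List the recorded AEs by patient and arm, and say whether they were collected in the two non-insert arms. Keep the statement that there were none only if the listing shows none.
4. Reword the Conclusion to say that none of the named events was seen in 10 insert patients and that safety relative to topical steroids was not established, giving the interval of −25.9 to +27.8 points for IOP rises above 10 mmHg.
5. Replace the wrong row from source data, tabulate IOP by arm and visit, and confirm the count of rises above 10 mmHg from patient-level values.
6. State which AE recording rule was applied and how relatedness was judged.

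In the protocol, reconcile 5.1.3 with 6.2 and correct the reference to Section 7.

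The cost is a more modest safety statement, one corrected row and two tables. IOP is scheduled at all six visits, so no new data collection is needed for it. The three-arm AE listing depends on collection in the non-insert arms, which the schedule's row label leaves unclear. If it was not done, the report should say so.

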### **Statistical Analysis**

All statistical analysis was performed using Prism 9 software (GraphPad Software, Inc.). Repeated measures analysis of variance was performed to compare the values at each time point in each group. Post hoc analyses were also performed with Bonferroni correction to directly compare the mean values at each time point in comparison to baseline. A *P* value less than 0.05 was considered statistically significant.

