To evaluate symptoms, a subjective questionnaire, DEQ-5, was administered at each time point. At baseline, the mean DEQ score was  $14.1 \pm 4.0$ ,  $14.4 \pm 2.4$  and  $14.4 \pm 3.7$  in the dextenza, loteprednol and cyclosporine monotherapy groups, respectively. In the dextenza group, the mean DEQ score improved to  $10.6 \pm 4.6$  ( $P = 0.22$ ),  $11.3 \pm 4.5$  ( $P = 0.19$ ) and  $10.3 \pm 6.3$  ( $P = 0.20$ ) and weeks 4, 8 and 12, respectively but the change was not statistically significant. In the loteprednol group, there was a significant improvement in the DEQ score with a mean score of  $11.0 \pm 2.4$  ( $P < 0.01$ ),  $9.1 \pm 4.0$  ( $P < 0.01$ ), and  $10.2 \pm 3.8$  ( $P < 0.01$ ), at weeks 4, 8 and 12, respectively. Similarly, there was an improvement in the DEQ score in the cyclosporine monotherapy from baseline at weeks 8 ( $10.6 \pm 2.6$ ,  $P < 0.01$ ) and 12 ( $9.4 \pm 3.1$ ,  $P < 0.01$ ), but the change at 4 weeks ( $12.2 \pm 2.2$ ,  $P = 0.39$ ) was not statistically significant.

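### The SAP Discussion says nothing was significant and links symptom relief to the steroid combination, but DEQ-5 also improved significantly on cyclosporine alone and no reported analysis compares the arms

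*SAP*

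**What the plan says.** The SAP's Statistical Analysis section sets the threshold: a P "value less than 0.05 was considered statistically significant". It describes repeated measures analysis of variance within each group, and then: "Post hoc analyses were also performed with Bonferroni correction to directly compare the mean values at each time point in comparison to baseline". It describes no comparison between groups.

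The DEQ-5 paragraph at the end of the SAP Results gives three outcomes:

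- **Loteprednol plus cyclosporine:** "there was a significant improvement in the DEQ score with a mean score of" 11.0, 9.1 and 10.2 at weeks 4, 8 and 12, each with P<0.01, from a baseline of 14.4.
- **Cyclosporine monotherapy:** "Similarly, there was an improvement in the DEQ score in the cyclosporine monotherapy from baseline at weeks 8" (10.6, P<0.01) and 12 (9.4, P<0.01), from a baseline of 14.4. Week 4 (12.2, P=0.39) was not significant.
- **Insert plus cyclosporine:** 10.6, 11.3 and 10.3 from a baseline of 14.1, with P=0.22, 0.19 and 0.20.

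The Discussion says that "patients in the loteprednol group reported a significant improvement in symptoms as measured by the DEQ-5 questionnaire", and of the insert arm: "The dextenza group also noted an improvement in symptoms, but the change was not statistically significant". It continues: "An improvement in symptoms with a combination of cyclosporine 0.05% and corticosteroids corroborates what has previously been reported". The next paragraph contains the clause "Although this present study did not yield any significant results". Neither the Discussion nor the Conclusion mentions the monotherapy DEQ-5 result.

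**The concern.** There are two defects. First, the clause about no significant results has no qualifier. It conflicts with the Results and with the Discussion's own preceding paragraph on loteprednol.

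Second, the Discussion describes symptom change in the two steroid arms and relates it to earlier reports on the combination, but leaves out the arm without a steroid. That arm is the comparator for the protocol's symptom hypothesis (section 1.2), that adding the insert gives greater symptomatic improvement than pharmacotherapy alone. Improvement from baseline within a steroid arm cannot separate a steroid effect from a cyclosporine effect, regression to the mean, or response to being treated open-label. Nor is significance in one arm and not in another a comparison of the arms.

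At stake is what a reader takes from the trial about symptoms. From the Discussion alone, the reader would not learn that patients without a steroid also improved significantly.

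**Working it through.** **Inputs.** DEQ-5 means and SDs come from the SAP Results, and patients per arm (10 insert, 11 loteprednol, 9 monotherapy) from the start of the Results. The scale runs from 0 to 22 and higher is worse (SAP, Main Outcome Measures), so a negative change is improvement.

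**Step 1: the stated P values against the clause.** Nine DEQ-5 comparisons with baseline are reported (three arms, three visits). Five have P<0.01: three for loteprednol and two for monotherapy. All five meet the SAP's 0.05 threshold.

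**Step 2: can the stated P values be reproduced?** Not exactly. The documents do not give the within-patient correlation r, whether n counts patients or eyes, or the number of comparisons in the Bonferroni correction. A paired t test from summary data uses

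SD_change = sqrt(SD0² + SD1² − 2·r·SD0·SD1).

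Take patient n and a threefold correction. For the insert at week 12 with r=0.45, SD_change = sqrt(16.00 + 39.69 − 22.68) = 5.745, and t = −3.8/(5.745/√10) = −2.09. The unadjusted P is 0.066 and the corrected P is 0.198, against 0.20 reported. At r=0.5, week 12 gives P=0.006 for loteprednol and 0.007 for monotherapy, in line with P<0.01. Monotherapy at week 8 gives 0.032 at r=0.45 and 0.008 only at r=0.7. The reported values are attainable, but one common r does not fit them all.

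**Step 3: mean change from baseline.**

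| Arm | Week 4 | Week 8 | Week 12 |
|---|---|---|---|
| Insert | 10.6 − 14.1 = −3.5 | 11.3 − 14.1 = −2.8 | 10.3 − 14.1 = −3.8 |
| Loteprednol | 11.0 − 14.4 = −3.4 | 9.1 − 14.4 = −5.3 | 10.2 − 14.4 = −4.2 |
| Monotherapy | 12.2 − 14.4 = −2.2 | 10.6 − 14.4 = −3.8 | 9.4 − 14.4 = −5.0 |

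**Step 4: between-arm difference in change.** Welch interval: SE = sqrt(SD_change,A²/nA + SD_change,B²/nB). Example, insert minus monotherapy at week 12 with r=0.45: the monotherapy SD_change is sqrt(13.69 + 9.61 − 10.32) = 3.602, so SE = sqrt(5.745²/10 + 3.602²/9) = 2.178. With 15.3 degrees of freedom the multiplier is 2.128. The difference is −3.8 − (−5.0) = +1.2, and the interval is 1.2 ± 4.63, that is −3.4 to 5.8.

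| Contrast | Week | Difference | 95% CI, r=0.45 | 95% CI, r=0 | 95% CI, r=0.7 |
|---|---|---|---|---|---|
| Loteprednol − monotherapy | 4 | −1.2 | −4.1 to 1.7 | −4.95 to 2.55 | −3.46 to 1.06 |
| | 8 | −1.5 | −4.8 to 1.8 | −5.84 to 2.84 | −4.10 to 1.10 |
| | 12 | +0.8 | −2.6 to 4.2 | −3.65 to 5.25 | −1.76 to 3.36 |
| Insert − monotherapy | 4 | −1.3 | −5.1 to 2.5 | −6.39 to 3.79 | −4.24 to 1.64 |
| | 8 | +1.0 | −2.8 to 4.8 | −4.13 to 6.13 | −1.90 to 3.90 |
| | 12 | +1.2 | −3.4 to 5.8 | −4.87 to 7.27 | −2.40 to 4.80 |

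A negative difference favours the steroid arm. Every interval includes zero across the assumed range of r. The direction is mixed: loteprednol leads numerically at weeks 4 and 8, the insert at week 4 only, and monotherapy leads both at week 12.

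**The case against.** The Discussion does not conceal the loteprednol result; it reports it one paragraph before the disputed clause. That clause closes a paragraph about the insert. Read as a statement about the insert it is correct, because all three insert DEQ-5 P values are near 0.2 and the Results report no significant change in signs. This stands, and it reduces the first defect to a missing qualifier. But the clause refers to the whole study and to any result, so it needs one.

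The sentence on corroboration speaks of improvement on a combination and does not say that the combination beat monotherapy. This also stands. A reader might infer a claim of superiority that is not on the page. The criticism is narrower: without the monotherapy result, the sentence invites that inference and no reported test supports it.

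Week 12 may be the wrong place to look for a steroid effect. The protocol prescribes Lotemax for one month and describes insert release for up to 30 days, so week 12 falls about eight weeks after exposure. The Discussion describes the earlier evidence as quicker relief, and at week 4 loteprednol was significant while monotherapy was not. That pattern could fit faster relief, which is why all three visits belong in the report. The direct week 4 contrast, however, is −1.2 with an interval of −4.1 to 1.7 at r=0.45.

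**Conclusion.** The point holds for the Discussion's interpretation of symptoms. The clause about no significant results is wrong as worded, since five of the nine reported DEQ-5 comparisons have P<0.01. The account of steroid combination therapy omits the significant improvement without a steroid, and the described analysis cannot attribute the change to the steroid.

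Two stronger readings are tempting and unsupported. One is that cyclosporine alone did best, or as well as the steroid arms, because its week 12 fall was the largest (−5.0 against −4.2 and −3.8). That is a numerical lead at one visit; monotherapy had the smallest fall at week 4, and the largest fall at any reported visit was loteprednol at week 8. Intervals several points wide on either side establish neither superiority nor equality. The other is that the trial's Conclusion falls. It does not: the Conclusion rests on safety, asks for further study and cites no DEQ-5 result, and the Discussion opens by calling efficacy unclear.

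The interval widths rest on an assumed r, on patients as the unit, and on summary data rounded to one decimal. They are unadjusted for multiplicity and for baseline differences. Protocol section 3.1 calls the study non-randomized while the SAP says patients were randomized, so even exact contrasts would need care in causal wording.

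**What to change.** Replace the two Discussion sentences with text that says:

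1. the primary endpoint was not met in any arm;
2. DEQ-5 improved significantly from baseline in the loteprednol arm (weeks 4, 8 and 12) and the monotherapy arm (weeks 8 and 12), but not in the insert arm at those visits;
3. no added symptom benefit of either steroid over monotherapy was shown, and neither superiority nor equality is established.

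If the clause about no significant results is kept, limit it to the insert arm or to the primary endpoint.

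Report the between-arm differences in DEQ-5 change, with 95% intervals, at every reported visit. Compute them from patient-level data with the patient as the unit, and label them as added after the fact. The approximate values above show what to expect but should not be published in their place.

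The cost is a few sentences and six contrasts from data already held. The downside is that, with 9 to 11 patients per arm, the contrasts will be imprecise and will not settle whether a steroid helps early. No change to the Conclusion is needed on this account.

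### The SAP says the insert and loteprednol groups did alike and hints at uncompromised efficacy, but it reports no between-group comparison and the DEQ-5 data are too imprecise to show similarity or a difference

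*SAP*

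**What the plan says.** The SAP is written as a completed report. Three of its statements bear on how the insert compares with topical loteprednol.

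- Discussion, in the paragraph on sustained delivery: "both the topical steroid and intracanalicular dexamethasone groups in this present study offered similar results". The clause carries no qualifier.
- Conclusion, last sentence: after noting that further study is needed, it says "use of the dexamethasone insert may provide a means to optimize medication delivery without compromising safety or efficacy".
- Discussion, first paragraph: "the efficacy of this combination remains unclear based on the results of this pilot study".

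The method is given in the Statistical Analysis section: "Repeated measures analysis of variance was performed to compare the values at each time point in each group", followed by Bonferroni-corrected comparisons of each visit with baseline. No between-group test, difference or interval is described or reported. The protocol (section 1.2) hypothesises that adding the insert will be non-inferior to Restasis with Lotemax, but neither document gives a margin.

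**The concern.** A statement that two active groups gave similar results is a between-group claim. The analysis contains only within-group tests, and no sign changed significantly in any group. Two groups that each fail to change significantly have not been shown to be alike. The closing sentence then carries the idea of preserved efficacy into the message that readers will remember. In effect it answers in words the non-inferiority question that the protocol posed and the analysis never tested. It also sits badly with the Discussion's own statement that efficacy is unclear. A between-group analysis added elsewhere would not correct these sentences, so the text itself needs to change.

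**Working it through.** The documents give no between-group estimate, margin or power figure to reproduce, and no change scores. The check therefore starts from the printed DEQ-5 means and SDs.

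**Inputs** (SAP, Results). Groups: 10 patients on the insert; for the others, "22 eyes of 11 subjects in the loteprednol/cyclosporine group and 18 eyes of 9 subjects in the cyclosporine monotherapy group". DEQ-5 is one score per patient, so patients are the unit. All patients are assumed to contribute at each visit.

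| DEQ-5 mean (SD) | Insert, n = 10 | Loteprednol, n = 11 |
|---|---|---|
| Baseline | 14.1 (4.0) | 14.4 (2.4) |
| Week 4 | 10.6 (4.6) | 11.0 (2.4) |
| Week 8 | 11.3 (4.5) | 9.1 (4.0) |
| Week 12 | 10.3 (6.3) | 10.2 (3.8) |

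**Step 1, improvement from baseline.** Insert: 3.5, 2.8, 3.8. Loteprednol: 3.4, 5.3, 4.2. Ratios: 3.5/3.4 = 1.03, 2.8/5.3 = 0.53, 3.8/4.2 = 0.90.

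**Step 2, SD of change.** SD_change = √(SD₀² + SD_t² − 2·r·SD₀·SD_t). The correlation r between baseline and visit is not reported, so it is assumed. At week 8 with r = 0.5:
- Insert: √(16 + 20.25 − 18) = √18.25 = 4.27
- Loteprednol: √(5.76 + 16 − 9.6) = √12.16 = 3.49

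**Step 3, Welch interval.** SE = √(18.25/10 + 12.16/11) = 1.71; df = 17.4; t = 2.106. Difference 5.3 − 2.8 = 2.5, and 2.5 ± 3.6 gives -1.1 to 6.1.

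The same steps at each visit (positive = insert worse):

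| Week | Difference | 95% CI, r = 0.5 | Upper limit, r = 0.2 | Upper limit, r = 0.7 | Loteprednol improvement |
|---|---|---|---|---|---|
| 4 | -0.1 | -3.4 to 3.2 | 4.1 | 2.5 | 3.4 |
| 8 | +2.5 | -1.1 to 6.1 | 7.0 | 5.4 | 5.3 |
| 12 | +0.4 | -3.9 to 4.7 | 5.7 | 3.9 | 4.2 |

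Even at r = 0.7, the upper limits are 2.5/3.4 = 73%, 5.4/5.3 = 101% and 3.9/4.2 = 93% of the loteprednol improvement.

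**Step 4, is the range of r reasonable?** Take the insert group's printed P values (0.22, 0.19, 0.20) as paired t-tests on 10 patients. A Bonferroni factor of 3 implies r of about 0.20, 0.52 and 0.45; a factor of 5 implies about 0.40, 0.64 and 0.61. All lie within 0.2 to 0.7. The factor and the unit of analysis are not stated, so r cannot be pinned down.

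**Step 5, what the sample could resolve (illustrative).** The pooled week-8 SD is √((9·4.5² + 10·4.0²)/19) = 4.24. Power to detect 2.5 points with 10 and 11 patients is about 27%. For an assumed non-inferiority margin of 2.5 points (80% power, one-sided 2.5%), n per group = 2·4.24²·(1.96 + 0.84)²/2.5², or about 46. Assumed margins of 1 and 3 points need 283 and 32.

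**Staining.** Corneal change in the insert group is 0.1, 0.0 and 0.2 from the Results text (baseline 0.5), or 0.0, -0.1 and 0.1 from Table 2 (baseline 0.6). In the loteprednol group it is 0.1, -0.8 and -0.2. At baseline 70% and 64% of eyes had no corneal staining, so agreement on this scale says little.

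**The case against.** The text is milder than a quick reading suggests. The similarity remark is a concessive clause leading into delivery advantages that the report itself calls theoretical; it does not claim equivalence or non-inferiority. The Conclusion is hedged. The report calls itself a pilot, admits a small sample, and says that no group met the primary endpoint. It also says that the DEQ-5 gain was significant on loteprednol and not on the insert. Uncertainty about whether the combination works can coexist with two groups looking alike. At weeks 4 and 12 the mean DEQ-5 improvements are indeed close.

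Much of this stands. A reader might infer that the SAP firmly concludes that efficacy is preserved; the wording of its last sentence does not go that far. A reader might also infer from week 8 that the insert gives only half the benefit. That is the least favourable of the three reported visits, and its difference is compatible with zero at every correlation tried (P about 0.31 at r = 0 to 0.08 at r = 0.7). Counting eyes (20 and 22) would bring it to P = 0.046 at r = 0.5, but that counts each patient's single score twice. Nor does P < 0.01 in one group beside P of about 0.2 in the other show that the groups differ. Finally, it would be too strong to say that the upper limits exceed the whole loteprednol improvement throughout: that fails at week 4 with r = 0.5 and at week 12 with r = 0.7.

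What the objection does not supply is an estimate behind the similarity clause, which is stated flatly as a result of this study. General caveats about sample size do not turn it into a supported statement.

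**Conclusion.** The point holds as a lack of evidence for similarity, not as evidence that the insert is worse. The DEQ-5 intervals include zero at all three reported visits. They also allow a loteprednol advantage of 3.2, 6.1 and 4.7 points at r = 0.5, against loteprednol improvements of 3.4, 5.3 and 4.2. Over r = 0.2 to 0.7 the upper limits run from 4.1 to 2.5, 7.0 to 5.4 and 5.7 to 3.9. The study therefore cannot exclude losing most of the comparator's improvement, and it does not show that any is lost.

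This rests on printed summary data, an assumed correlation, patients as the unit and complete follow-up. The intervals cover sampling error only. The protocol calls the study non-randomised and the SAP calls it randomised, so bias from allocation is a separate matter. The exact limits would change with patient-level data. The finding that no between-group comparison supports the wording would not.

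**What to change.** 1. In the Discussion, replace the similarity clause with patient-level between-group differences in change from baseline, insert minus loteprednol, with 95% CIs. Give them for DEQ-5 and for corneal and conjunctival staining at weeks 1, 2, 4, 8 and 12. For staining, allow for two eyes per patient, and first reconcile the insert group's baseline corneal score (0.5 in the text, 0.6 in Table 2).
2. State that the study neither shows nor excludes a clinically relevant difference from topical loteprednol, and that non-inferiority was not tested because no margin was set.
3. Remove the words *or efficacy* from the last sentence of the Conclusion, so that it agrees with the Discussion's statement that efficacy is unclear.

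The protocol schedules these measurements at every visit, so the cost is a short analysis of existing data and a few sentences of text. The downside is a conclusion less favourable to the insert.
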